### 15.4 Analysis of Secondary Endpoints

Constipation is defined as <3 bowel movements in the past week and/or Bristol Stool type 1 or 2. The secondary endpoint upon which the sample size is based is the number (%) of enrolled subjects with any occurrence of constipation during 1 month of follow-up (the period prevalence). Treatment for GI symptoms and constipation will be summarized based on the percentage of enrolled subjects receiving and initiating treatment at time of enrollment visit. To evaluate whether CF subjects are adequately treated, the number and percentage of subjects with GI symptoms and constipation on treatment will be reported. All GI related treatments will be classified by medication type/class.

Individual GI symptoms will be extracted from the PAC-SYM and PAGI-SYM questionnaires. For each GI symptom, frequency and severity will be summarized at each assessment as follows: number (%) of subjects with GI symptom, severity of GI symptom (mean score and distribution of severity score) and change in severity scores from the enrollment visit by whether subjects were receiving treatment.

Mean overall (and by sub-scale) PRO scores for PAC-SYM, PAGI-SYM and PAC-QOL at scheduled assessments will be reported including evaluation of within and between subject variability. Group comparisons of mean scores by subjects receiving/not receiving treatment and by those with/without constipation will also be made. Absolute change in PRO scores from enrollment visit to scheduled assessments will be reported based on subjects receiving/not receiving treatment for constipation. To examine these effects, figures displaying mean PRO scores by scheduled assessment will be created. Additionally, mixed effects models for repeated measures will be fit with PRO scores as the outcome and covariates for visit, treatment, pancreatic status, age group and the interaction between treatment and visit.

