## 15.5 Analysis of Missing Data

Detailed summaries of missing data including the number and percentage of scheduled assessments with at least one of the four PROs completed will be provided. For each PRO, the percentage of scheduled assessments with fully completed PROs will also be provided. Other missing data methods to examine sensitivity and robustness of study results for the primary and key secondary endpoints will be described in the SAP. To minimize missing data, subjects will receive reminder notifications to complete their scheduled assessment.

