## 15.7 Sample Size

[figure not shown]
Sample size estimates for this study are based on two criteria:

- a. To assess feasibility and ensure representativeness of the enrolled CF subjects
- b. To estimate prevalence of GI symptoms (specifically constipation)

Period prevalence is defined as the proportion of subjects with symptom over an interval of time. Estimates of constipation prevalence in CF patients varies in the literature. A recent 2017 publication (7) showed the period prevalence of constipation over 3 months was 31% (32% adults; 30% children). Another 2010 publication (3) estimated prevalence of constipation in CF patients age  $\leq$  18 years in the Netherlands at 20% (annual assessment) using the ESPGHAN definition. Note that an epidemiologic review of constipation prevalence in the general population (non-CF) in North America ranged from 1.9% to 27.2% with most estimates from 12%-19% (19). Therefore, 10% will serve as the lower bound estimate of constipation prevalence. The sample size estimate for CF patients in the GALAXY study is based on a prevalence of constipation over a 1 month period in the 20% - 30% range (25% average).

Sample size estimates are based on 95% confidence intervals (C.I.) half-widths (i.e., width of one arm of the 95% CI) for proportions. While constipation is one symptom of interest, it is difficult to specify an exact prevalence estimate over a 1 month period utilizing the study specific definition of constipation. In addition, the occurrence of other GI symptoms is also of interest and will occur at varying rates. Therefore, the figure below shows what the sample size (y-axis) is for varying half-width sizes (x-axis) when prevalence estimates range between 10% to 50% (maximum). Approximately 400 subjects are needed to estimate a prevalence of constipation of 25% with a 95% C.I. half-width of 4.5% (95% C.I. = 20.5%, 29.5%) and assuming a 12% missing data rate.

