3.4 Secondary Endpoints

3.4.1 The feasibility of ePRO surveys conducted outside-the-clinic setting:

1. At each scheduled outside-the-clinic assessment, number (%) of participants with at least one PRO fully completed
2. For each PRO, number (%) of participants with fully completed questionnaires at each scheduled outside-the-clinic assessment and overall
3. Number (%) of completed PROs by age and site

The corresponding analyses are outlined in Appendix A, Section A.3.

3.4.2 Prevalence and variability of GI symptoms:

Evaluation of PRO scores overall and by sub-scale at scheduled assessments:

4. Mean PRO score for PAC-SYM, PAGI-SYM, and PAC-QOL
5. Within- and across-participant variability of PRO scores

Descriptive statistics will be used to visually summarize the total scores and domain scores over time, and by age group. Longitudinal summaries will be provided, using mixed-effect models with participant-specific random intercepts. The corresponding analyses are outlined in Appendix A, Section A.4.

Evaluation of the prevalence of protocol-defined constipation:

6. Number (%) of enrolled participants with any occurrence of protocol-defined constipation during 1 month of follow-up (the period prevalence)

Descriptive statistics will be used to summarize the protocol-defined constipation, as well as other information from the disease-specific questionnaire over time, and by age group. The corresponding analyses are outlined in Appendix A, Section A.5.

Evaluation of the frequency and severity of each GI symptom at scheduled assessments and overall:

7. Number (%) of participants with presence of GI symptom
8. Distribution of severity scores of GI symptom
9. Mean severity score of GI symptom
10. Mean severity score of GI symptom
11. Distribution of stool frequency and type by Bristol Stool Scale

12. Change in distribution of GI symptoms and stool frequency/type from baseline visit overall

Pre-specified GI symptoms of interest, i.e. particular questions from the ePROs, are identified. Descriptive statistics will then be used to summarize the distributions of these GI symptoms overall, by age group, and the change from baseline. The corresponding analyses are outlined in Appendix A, Section A.5.

Evaluation of PAC-SYM, PAGI-SYM, and PAC-QOL scores by protocol-defined constipation:

13. Mean total and domain scores (also mean difference and 95% confidence interval) comparing participants with and without protocol-defined constipation

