[1] 'All Enrolled Participants' are those who met study eligibility criteria and fully completed at least ePRO at baseline visit (Visit 1).

[2] Pancreatic Insufficient is defined as PERT use and/or fecal elastase or other diagnostic test at baseline.

Note on missing demographic data

A.3 Summary of ePRO Completion

Exhibit 3.1.x Completion of ePRO Questionnaires – [All or Subgroups Defined by Age here]

This table summarizes ePRO completion rate across baseline and follow-up weeks. “Fully completed” a questionnaire is defined as having responded to all questions with no missing responses.

Week	PAC-SYM	PAGI-SYM	PAC-QOL	Disease-Specific	Fully Completed at Least One ePRO	Fully Completed all ePROs
Baseline (N=n)	n (%)					
Week 1 (N=n)	n (%)			X		
Week 2 (N=n)	n (%)			X		
Week 4 (N=n)	n (%)					
All follow-up weeks	n (%)					

Note: PAC-QOL was only collected at Baseline and Week 4.

Exhibit 3.1.1 Completion of ePRO Questionnaires – All Participants

Exhibit 3.1.2 Completion of ePRO Questionnaires – Age <18 Years

Exhibit 3.1.3 Completion of ePRO Questionnaires – Age ≥18 Years

Exhibit 3.2.1 Missing Data for ePROs by Follow-up Week and Participant

This figure helps to visualize the number of not-fully-completed ePROs at each week by participant. Data for each study participant is represented by a row. The color indicates the number of not-fully-completed ePROs at each week. For example, at baseline, enrolled participants are defined as those with eligibility and fully completed at least one ePRO. Hence, for each participant at baseline, there can only be zero, one, two, or three ePROs missing. Similarly, since PAC-QOL is not collected at Weeks 1 and 2, there can only be zero, one, two, or three ePROs missing.

[figure not shown]

Exhibit 3.2.2 Missing Data for ePROs by Participant with Age < 18
Exhibit 3.2.3 Missing Data for ePROs by Participant with Age ≥ 18

Exhibit 3.3 Completion of ePROs by Site

This table summarizes ePRO completion by site

Site	Number of Participants	Fully Completed at Least One ePRO at All Follow-Up Weeks (Weeks 1,2 & 4)	Fully Completed all ePROs at All Follow-Up Weeks (Weeks 1, 2 & 4)
Site 1			
Site 2			
...			
Site s			
Overall			

A.4 Summary of PAC-SYM, PAGI-SYM, and PAC-QOL Scores

Exhibit 4.1 Distributions of Total Scores for PAC-SYM, PAGI-SYM, and PAC-QOL for All Participants

This figure summarizes the total scores for PAC-SYM, PAGI-SYM, and PAC-QOL at each week and overall, for all participants.

[figure not shown]

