Stool Symptoms (NN=nn)									
PAGI-SYM Total Score (NN=nn)									
Nausea/Vomiting (NN=nn)									
Post-Prandial Fullness/Early Satiety (NN=nn)									
Bloating (NN=nn)									
Upper Abdominal Pain (NN=nn)									
Lower Abdominal Pain (NN=nn)									
Heartburn/Regurgitation (NN=nn)									
PAC-QOL Total Score (NN=nn)									
Physical Discomfort (NN=nn)									
Psychosocial Discomfort (NN=nn)									
Worries and Concerns (NN=nn)									
Satisfaction (NN=nn)									

A.5 Summary of Prevalence and Variability of GI Symptoms

Exhibit 5.1.1 Summary of Disease-Specific Questionnaire – All Participants

This table summarizes the GI disease-specific questionnaire for all participants. All questions were based on patient's experience in the last week.

		Baseline (N=n)	Week 1 (N=n)	Week 2 (N=n)	Week 4 (N=n)
Bowel Movements	<3 Bowel Movements ≥3 Bowel Movements		n (%)		
Self-Described Bowel Pattern:	Normal Constipated Diarrhea Alternating Constipation and Diarrhea				
Bristol Stool Scale ^[1] :	1 (Hard Lumps) – 2 3 – 5 6 – 7 (Watery) Missing				
Leakage of Stool:	Yes				
Protocol-Defined Constipation ^[2]:	Yes				

[1] Question for Bristol Stool Scale: describe what your stool looked like on most days in the last week when you had a bowel movement?

[2] Protocol-defined constipation is defined as less than 3 bowel movements and/or Bristol Stool type 1 or 2 in the past week

Exhibit 5.1.2 Summary of Disease-Specific Questionnaire – Age < 18

Exhibit 5.1.3 Summary of Disease-Specific Questionnaire – Age ≥ 18

Exhibit 5.2.1 Demographics and Baseline Characteristics by Protocol-Defined Constipation at Baseline.

This table summarizes demographics and baseline characteristics, stratified by protocol-defined constipation at Baseline Visit.

	Protocol-Defined Constipation at Baseline		All Enrolled Participants (N=n)	Fully Completed at Least One ePRO at all Follow-up Weeks (N=n)	CF Registry (N=n)
	Yes (N=n)	No (N=n)			
Sex at Birth, n (%)	Female				
	Male				
Age Distribution, n (%)	<6 years				
	≥6 – 12 years				
	≥12 – 18 years				
	≥18 – 24 years				
	≥24 – 30 years				
	≥30 years				
	Mean (SD)				
	Median				
	Min, Max				
Race, n (%)	White				
	American Indian or Alaska Native				
	Black or African American				
	More than One Race				
	Unknown or Not Reported				
Ethnicity, n (%)	Hispanic or Latino				
	Not Hispanic or Latino				

CF Therapeutics Development Network Coordinating Center
GALAXY-OB-18

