		Protocol-Defined Constipation at Baseline		All Enrolled Participants (N=n)	Fully Completed at Least One ePRO at all Follow-up Weeks (N=n)	CF Registry (N=n)
		Yes (N=n)	No (N=n)			
Genotype, n (%)	F508 Heterozygous F508 Homozygous Other/Unknown					
Mutation Class, n (%)	I-III IV-V Unknown					
Sweat Chloride at Diagnosis (mEq/L)	Mean (SD)					
Weight (kg)	Mean (SD)					
Height (cm)	Mean (SD)					
Pancreatic Sufficiency[1], n (%)	Insufficient Sufficient Unknown					
Modulator Use, n (%)	None Ivacaftor Ivacaftor/Lumacaftor Ivacaftor/Tezacaftor Ivacaftor/Tezacaftor/Elexacaftor					

[1] Pancreatic Insufficient is defined as PERT use and/or fecal elastase or other diagnostic test at baseline.
Note on missing demographic data

Exhibit 5.2.2 Summary of Period-Prevalence of Constipation with Disease-Specific Questionnaire Fully Completed at all Weeks

This table summarizes the period-prevalence of protocol-defined constipation, as well as other definitions of constipation. Only participants who fully completed the disease-specific questionnaire at baseline and all follow-up weeks were considered. Period prevalence is defined as occurrence of the symptom at any time from baseline to week 4.

	Age <18 Years (N = n)	Age ≥18 Years (N = n)	All Participants (N = n)
Protocol-Defined Constipation ^[1] :	% (95% CI)		
Self-Described Constipation ^[2]			
Constipation			
Alternating Constipation and Diarrhea			
Alternative Definition:			
Definition 1			
...			
Definition d			

[1] Protocol-defined constipation is defined as less than 3 bowel movements and/or Bristol Stool type 1 or 2 in the past week

[2] Self-described constipation is based on the second question on the disease-specific questionnaire

Note: See Appendix B for discussion regarding alternative definitions of constipation.

Exhibit 5.2.3 Summary of Period-Prevalence of Constipation with Disease-Specific Questionnaire Fully Completed at least once

Similar table as above with consideration of participants who fully completed the disease-specific questionnaire at least once.

Exhibit 5.3.1 Summary of GI Symptoms from PAC-SYM, PAGI-SYM, and PAC-QOL

This table summarizes the GI symptoms based on prespecified questions from PAC-SYM, PAGI-SYM, and PAC-QOL questionnaires. All questions were based on patient's experience in the last week.

	Baseline	Week 1	Week 2	Week 4	Overall [1]
Symptom 1					
N [2]					
Absent, n (%)					
Mild, n (%)					
Moderate, n (%)					
Severe, n (%)					
Very Severe, n (%)					

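### Period prevalence of constipation has no named main estimate in the enrolled set: Exhibit 5.2.2 drops observed cases who have an incomplete week, and Exhibit 5.2.3 reads low

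*SAP*

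**What the plan says.** Protocol 15.4 gives the endpoint its weight: "The secondary endpoint upon which the sample size is based is the number (%) of enrolled subjects with any occurrence of constipation" over one month. SAP 3.4.2 item 6 repeats it for enrolled participants and points to Appendix A.5. There, period prevalence is counted at any time from baseline to week 4, over four assessments (baseline, weeks 1, 2 and 4).

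Two tables report it:
- Exhibit 5.2.2: "Only participants who fully completed the disease-specific questionnaire at baseline and all follow-up weeks were considered".
- Exhibit 5.2.3: "Similar table as above with consideration of participants who fully completed the disease-specific questionnaire at least once".

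Neither is called main, primary or sensitivity. Neither population is the enrolled set. SAP 2.3 requires only one of the four questionnaires to be complete at baseline, and it need not be the disease-specific one.

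On completeness, Exhibit 3.1.x says that to have fully completed "a questionnaire is defined as having responded to all questions with no missing responses". Constipation itself rests on two items, bowel-movement frequency and Bristol type. The Bristol item asks participants to "describe what your stool looked like on most days in the last week when you had a bowel movement" (Exhibit 5.1.1, footnote 1).

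On missing data, protocol 15.7 sizes the study "assuming a 12% missing data rate", without saying whether that is per participant or per visit. Protocol 15.5 leaves to the SAP "Other missing data methods to examine sensitivity and robustness of study results for the primary and key secondary endpoints". The SAP supplies completion summaries, the two tables above, and Unknown rows in Exhibits 6.3.1 and 6.3.2. It gives no imputation, weighting or bounds for period prevalence.

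**The concern.** With an any-occurrence endpoint, one positive week settles the outcome. Exhibit 5.2.2 nevertheless removes a participant with a recorded positive week if another week is incomplete. That discards known outcomes. It costs precision when missingness is unrelated to constipation, and can bias the estimate in either direction when it is related.

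Exhibit 5.2.3 keeps nearly everyone but states no rule for unobserved weeks. Without adjustment they can only fail to add cases, so the table is a lower bound for participants with at least one completed questionnaire. It is not strictly a lower bound for all enrolled, because some of those may have none.

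The estimate that justifies 400 subjects therefore has two versions and no named headline, and neither version matches the stated population.

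**Working it through.** **The plan's own figure.** Protocol 15.7: p = 0.25, half-width 0.045, 12% missing.
- n = 1.96² × 0.25 × 0.75 / 0.045² = 355.7, so 356.
- Inflated: 356/0.88 = 405, or 356 × 1.12 = 399. The stated 400 reproduces.
- Conversely, 400 × 0.88 = 352 evaluable. The Wilson half-width at 25% is 4.51 points for n = 352, 5.11 for n = 273 and 4.23 for n = 400.

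**Model (assumed).** Weekly status is beta-binomial over four assessments with pairwise correlation ρ = 0.5, and period prevalence is fixed at 25%. With ρ = 0.5 the beta parameters are p and b = 1 − p. Setting b(b+1)(b+2)(b+3)/24 = 0.75 gives b = 0.868 and weekly prevalence p = 0.132. The chance of at least one positive is then 0.132, 0.189, 0.224 and 0.250 over one, two, three and four assessments. Baseline is taken as observed.

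**Scenario (b): 12% of participants lose all follow-up.**
- 5.2.2 keeps 352, ±4.5 points, and reads 25%.
- Observed cases dropped: 48 × 0.132 = 6.3.
- 5.2.3 reads 0.88 × 0.250 + 0.12 × 0.132 = 23.6%.

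**Scenario (a): 12% of follow-up visits lost independently.**
- 5.2.2 keeps 400 × 0.88³ = 273, ±5.1 points, and reads 25%.
- The chances of three, two, one and no follow-ups observed are 0.681, 0.279, 0.038 and 0.002.
- 5.2.3 reads 0.681 × 0.250 + 0.279 × 0.224 + 0.038 × 0.189 + 0.002 × 0.132 = 24.0%, that is 96 observed cases per 400.
- 5.2.2 retains 273 × 0.25 = 68 of them and drops 28.

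With ρ = 0.3 or 0.7, 5.2.3 reads 23.2% or 24.0% in (b) and 23.7% or 24.4% in (a). The cases dropped are 5 or 8 in (b), and 27 of 95 or 29 of 98 in (a).

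**Bounds at ρ = 0.5.** The lower bound counts observed cases only; the upper counts every undetermined participant as a case.
- (a) 24.0% to 1 − 0.681 × 0.75 = 48.9%.
- (b) 23.6% to 1 − 0.88 × 0.75 = 34.0%.

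**Assumed links between constipation and missingness (not in the documents).**
- (c) Constipated weeks missed twice as often (24% against 12%): 5.2.2 reads 21.1% and 5.2.3 reads 23.0%.
- (d) Constipated weeks missed half as often (6% against 12%): 5.2.2 reads 27.0% and 5.2.3 reads 24.5%.
- Bristol item blank in 5% or 10% of constipated weeks, nothing else missing: 5.2.2 reads 23.2% or 21.3%, and 5.2.3 reads 24.6% or 24.0%.

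**Multiple imputation in all 400.** This was simulated from observed weeks only, with 20 imputations and 2,500 studies per setting. It reads 25.0% ±4.4 in both (a) and (b), 24.0% in (c) and 25.5% in (d).

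| | 5.2.2 | 5.2.3 | Imputed |
|---|---|---|---|
| (a) | 25.0% | 24.0% | 25.0% |
| (b) | 25.0% | 23.6% | 25.0% |
| (c) | 21.1% | 23.0% | 24.0% |
| (d) | 27.0% | 24.5% | 25.5% |

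**The case against.** The best defence is that the sample size fits a complete-case reading: 400 × 0.88 = 352, close to the 356 needed. If loss clusters within participants, as is plausible for electronic questionnaires, Exhibit 5.2.2 is unbiased at the planned precision and imputation adds little. This stands. A reader might infer from the 273 figure that planned precision is lost. That needs 12% to be per visit and independent, which the documents do not say.

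A reader might also infer that Exhibit 5.2.2 is biased. The documents do not support this. The readings in (c) and (d) come from assumed links, and (c) also raises overall missingness to 13.6%, above the plan's 12%. The Bristol route is only a possibility. The item may offer an answer for a week with no bowel movement, and Exhibit 6.3.2 lists an incomplete questionnaire and a blank question 2 separately, so the SAP's use of the term may not be uniform.

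Nor can one say that imputation beats both tables everywhere. In (d) it misses 25% by 0.5 points upward and Exhibit 5.2.3 misses by 0.5 downward. In (c) its interval covers the truth in 88.5% to 93.6% of simulated studies, much like the 86.9% to 93.4% for Exhibit 5.2.3 in (a) and (b). The simulation did not include the age and treatment covariates recommended below.

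Finally, protocol 15.5 is not simply unmet. Exhibit 6.3.1 shows Unknown weeks by baseline constipation, and its all-follow-up row counts anyone with one positive week. Both period-prevalence tables are prespecified, and the endpoint is descriptive. What remains is that no main estimate is named, that observed cases leave Exhibit 5.2.2, and that the two tables need not bracket the truth: in (c) both read below 25%.

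**Conclusion.** The point holds in a limited form and should be fixed. The endpoint behind the sample size is defined in enrolled participants, but it is reported only in two other populations, with no main estimate. Exhibit 5.2.2 discards about 6 observed cases in (b), or about 28 of 96 in (a), with half-widths of 4.5 and 5.1 points. Exhibit 5.2.3 reads about 1.4 points low in (b) and 1.0 in (a), within the planned half-width.

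These sizes rest on 25% prevalence, 12% missing and 400 subjects from the protocol, and on an assumed weekly correlation of 0.5. The gain from the fix over 5.2.2 is small if loss clusters within participants. Over 5.2.3 it is about 1 to 1.5 points, with none if constipated weeks are missed less often. Confidence is high on what the tables do. The documents do not show a link between constipation and missingness, so no claim of actual bias in Exhibit 5.2.2 is made. Protocol 15.5 is partly met.

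**What to change.** 1. Derive weekly status from the two defining items: constipated if either answered item is positive; not constipated only if both are answered and negative; otherwise unknown. If a Bristol blank occurs in a week that is positive on frequency, this rule recovers the case without imputation.
2. Count a participant as a case if any observed week is positive.
3. Name one main estimate in all enrolled participants, with multiple imputation of unknown weeks from observed weeks, age group and baseline constipation treatment. Do not simply drop undetermined participants (about 99 per 400 in (a), 42 in (b)): cases would be kept preferentially, and the estimate would read about 32% in (a) and 26% in (b).
4. Report Exhibit 5.2.2, Exhibit 5.2.3 (labelled as a lower bound for its own population) and the lower and upper bounds as sensitivity analyses.
5. State that ±4.5 points applies to about 352 evaluable participants.

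The cost is SAP wording and modest programming, with no new data. Imputation adds a missing-at-random assumption; the bounds show how much rests on it.

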#### Estimate the prevalence and variability of GI symptoms:

- Evaluate prevalence of protocol-defined constipation:
  4. Number (%) of enrolled subjects with any occurrence of constipation during 1 month of follow-up (the period prevalence)
- Evaluate frequency and severity of each GI symptom at scheduled assessments and overall:
  5. Number (%) of subjects with presence of GI symptom

6. Distribution of severity scores of GI symptom
7. Mean severity score of GI symptom
8. Distribution of stool frequency and type by Bristol Stool Scale
9. Change in distribution of GI symptoms and stool frequency/type from enrollment visit overall and by whether subjects were receiving treatment

- Evaluate PRO scores overall and by sub-scale at scheduled assessments:
  10. Mean PRO score
  11. Within and across subject variability of PRO scores
  12. Mean PRO scores (also mean differences and 95% confidence interval) comparing subjects with constipation to those without constipation
- Evaluate alternative CF specific definitions of constipation:
  13. Examine alternative definitions of constipation that are CF specific based on correlation with PRO questionnaires and maximizing the area under the receiver operating characteristic curve (ROC curve) for PAC-SYM scores
  14. Number (%) reporting constipation based on patient self-assessment. Examine concordance of self-reported constipation against protocol/alternate definitions using Cohen's kappa coefficient

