Symptom Presence [3], n (%)					
Symptom Score [4], mean (sd)					
Symptom 2					
N [2]					
Absent, n (%)					
Mild, n (%)					
Moderate, n (%)					
Severe, n (%)					
Very Severe, n (%)					
Symptom Presence [3], n (%)					
Symptom Score [4], mean (sd)					

[1] Overall results were aggregated over all participants weeks. Overall symptom score is obtained from a longitudinal model.

[2] Number of participants who completed the question at each week

[3] Symptom presence is defined as checking any severity level other than "Absent"

[4] Symptom score is defined based on the scoring rubric of each ePRO (max of 4 for PAC-SYM and PAC-QOL, and max of 5 for PAGI-SYM)

Note: Selected symptoms were prespecified from PAC-SYM, PAGI-SYM, and PAC-QOL questionnaires (see Appendix C for the complete list of prespecified symptoms of interest). Scoring of symptoms range from either 0-4 (PAC-SYM and PAC-QOL) or 0-5 (PAGI-SYM)

Exhibit 5.3.2 Summary of GI Symptoms from PAC-SYM, PAGI-SYM, and PAC-QOL – Age < 18 Years
Exhibit 5.3.3 Summary of GI Symptoms from PAC-SYM, PAGI-SYM, and PAC-QOL – Age ≥ 18 Years

Exhibit 5.4.x Change from Baseline for [GI Symptom]

The following table shows the change in distribution for each symptom (including stool frequency/type) from baseline at each follow-up week.

		Week 1 (N =) [1] (Mean Score = , 95% CI =)						Week 2 (N =) [2] (Mean Score = , 95% CI =)						Week 4 (N =) [3] (Mean Score = , 95% CI =)																
		Absent		Mild		Moderate		Severe		Very Severe		Absent		Mild		Moderate		Severe		Very Severe		Absent		Mild		Moderate		Severe		Very Severe
Baseline (Mean = , 95% CI =)	n (%) Worsened	n (%)		n (%)		n (%)		n (%)		n (%)		n (%)		n (%)		n (%)		n (%)		n (%)		n (%)		n (%)		n (%)		n (%)		
		Moderate	Mild	Absent	Very Severe	Severe	Moderate	Absent	Very Severe	Severe	Moderate	Absent	Very Severe	Severe	Moderate	Absent	Very Severe	Severe	Moderate	Absent	Very Severe	Severe	Moderate	Absent	Very Severe	Severe	Moderate	Absent	Very Severe	
		n (%) Improved				n (%) No Change				n (%) Improved				n (%) No Change				n (%) Improved				n (%) No Change								

[1] Consider participants with both baseline and Week 1 data

[2] Consider participants with both baseline and Week 2 data

[3] Consider participants with both baseline and Week 4 data

Note: One table per each symptom; PAC-QOL only has data for Baseline and Week 4

Exhibit 5.4 Change in GI Symptoms from Baseline

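### The GI-symptom endpoint counts participants, but the Overall column of SAP Exhibits 5.3.1–5.3.3 counts participant-weeks, so no firm table gives the overall share of people with each symptom

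*SAP*

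**What the plan says.** - **Endpoint.** Protocol 5.2, item 5, is "Number (%) of subjects with presence of GI symptom". It stands under a line that asks for the "frequency and severity of each GI symptom at scheduled assessments and overall". SAP 3.4.2, item 7, repeats it as "Number (%) of participants with presence of GI symptom". The unit in both is the person.
- **Table.** SAP Appendix A.5, Exhibit 5.3.1, reports this endpoint; Exhibits 5.3.2 and 5.3.3 repeat it by age group. Footnote 1 says of the Overall column: "Overall results were aggregated over all participants weeks". Only the overall symptom score is treated differently, since it comes from a longitudinal model.
- **Denominator and rule.** Footnote 2 defines N as "Number of participants who completed the question at each week", which cannot serve the Overall column. Footnote 3 works on the single weekly response: "Symptom presence is defined as checking any severity level other than" the Absent category.
- **Constipation, same appendix section.** Exhibit 5.2.2 states: "Period prevalence is defined as occurrence of the symptom at any time from baseline to week 4". This matches Protocol 15.7: "Period prevalence is defined as the proportion of subjects with symptom over an interval of time". Exhibit 5.2.2 uses participants with all assessments complete, and Exhibit 5.2.3 those with at least one.

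**The concern.** In the Overall column, a participant with nausea at all four assessments adds four to the numerator, while one who has nausea once in four adds one. Someone who answers once carries a quarter of the weight of someone who answers four times. The resulting n (%) has the look of a count of people but is a count of weeks. SAP item 7 still says participants, so the SAP does not declare a change of endpoint; its table and its endpoint list simply differ.

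The prevalence of GI symptoms is a secondary objective, and Protocol 15.7 brings symptoms other than constipation into the same per-subject prevalence reasoning. If the Overall column for nausea, bloating or reflux were read beside the one-month constipation prevalence, the comparison would set an average week against any occurrence in a month.

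**Working it through.** **1. The plan's own figure.** The documents give no figure for overall symptom presence. The nearest is the sample size for the per-person constipation prevalence (Protocol 15.7: 25%, half-width 4.5 points, 12% missing, about 400 subjects).

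- n = 1.96² × 0.25 × 0.75 / 0.045² = 355.7, so 356.
- 356 / 0.88 gives 405; 356 × 1.12 gives 399.

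This agrees with about 400, so the sample size is not in question. It also confirms that the plan's precision statement is per person.

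**2. Is the person-level figure produced elsewhere?**

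- Exhibit 7.2 is at baseline only.
- The repeat of Exhibits 6.3–6.5 for specific symptoms (Appendix A.8) is conditional on data availability, and the all-weeks row it would copy covers follow-up weeks only.
- No other firm exhibit gives it for the PAC-SYM or PAGI-SYM symptoms in Appendix C.

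**3. Denominator.** There are four assessments (baseline, weeks 1, 2 and 4). With 400 participants, the Overall column has up to 4 × 400 = 1,600 participant-weeks, not 400 people.

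**4. Direction.** With complete data, the pooled percentage is the mean over people of (symptomatic weeks / 4). Each term is at most 1 for a person ever affected and 0 otherwise, so the pooled figure cannot exceed the share ever affected. They are equal only if everyone affected is affected at every assessment.

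With unequal completion this can fail. Take one participant symptomatic in 4 of 4 weeks and one symptom-free who answered once. The pooled figure is 4/5 = 80%; the share of people is 1/2 = 50%.

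**5. Size, as an illustration.** Assume a beta-binomial model with weekly prevalence p, within-person correlation ρ and complete data. Both p and ρ are assumptions. With s = (1 − ρ)/ρ, a = ps and b = (1 − p)s:

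P(any of 4) = 1 − ∏ (b + i)/(a + b + i), for i = 0 to 3.

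Example, p = 0.25 and ρ = 0.5: s = 1, a = 0.25, b = 0.75, so P = 1 − (0.75/1)(1.75/2)(2.75/3)(3.75/4) = 1 − 0.564 = 43.6%.

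| Pooled weekly % | ρ = 0.3 | ρ = 0.5 | ρ = 0.7 | ρ = 0.9 |
|---|---|---|---|---|
| 10 | 24.3 | 19.4 | 15.3 | 11.7 |
| 25 | 52.3 | 43.6 | 35.8 | 28.5 |
| 50 | 81.4 | 72.7 | 63.7 | 54.6 |
| 80 | 96.7 | 93.0 | 88.3 | 82.9 |

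Entries are the percentage of people ever affected. At pooled 25% the limits are 68.4% (ρ = 0) and 25% (ρ = 1). In reverse, the planned 25% one-month constipation prevalence would show as 10.3%, 13.2%, 16.8% or 21.8% if it were pooled over weeks, for ρ = 0.3, 0.5, 0.7 or 0.9.

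**6. Interval.** SAP section 3 prescribes Wilson intervals for symptom presence. On pooled weeks these would treat repeated answers as independent. The design effect is 1 + 3ρ, which is 2.5 at ρ = 0.5, so 1,600 weeks carry the information of 1,600 / 2.5 = 640 independent responses.

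**The case against.** Five points can be made for the SAP.

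- **Overall is undefined.** Neither document says that overall means any occurrence for symptoms. Protocol item 4 says so for constipation; item 5, just below, does not. Protocol 15.4 speaks only of symptom frequency at each assessment. This stands: any occurrence is the natural reading of an overall count of people, not an explicit one. But a count of weeks is not a number of participants under any reading.
- **The labels differ.** A reader might infer that the SAP presents two quantities under one name. It does not: Exhibits 5.2.2 and 5.2.3 are headed period prevalence, while Exhibit 5.3.1 says symptom presence, with a footnote on the pooling. What is missing is the denominator and a row label that shows the unit.
- **A fair comparison already exists.** A reader might infer that constipation can be compared with other symptoms only across different units. Exhibit 5.1.1 gives protocol-defined constipation at the same four times at which Exhibit 5.3.1 gives each symptom, both with one-week recall. Only the overall comparison is affected.
- **Decisions may not turn on it.** Protocol 1.2 has already chosen constipation as the first symptom to address, and the other symptoms share one unit among themselves. That weakens the consequence, though pooled ranks still depend on completion and persistence.
- **Pooled presence is legitimate.** It is a valid descriptive summary, and any occurrence may rank very common symptoms poorly because it nears the ceiling (93% to 97% at pooled 80% and ρ = 0.5 to 0.3). This argues for keeping both figures.

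**Conclusion.** The mismatch of unit is in the text and needs no model. Followed as written, the SAP reports a completion-weighted average weekly prevalence, without a denominator, where its endpoint list calls for a number of participants. That figure is not comparable with the constipation period prevalence.

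The size is not established. A reader might infer that the Overall column will fall far below the share of people affected. The documents do not support that, since they give neither weekly prevalence nor within-person correlation for any symptom. At pooled 25% the illustrated gap runs from about 27 points (ρ = 0.3) to 3.5 points (ρ = 0.9). It is zero if status never changes, and the order can reverse if symptomatic participants complete more weeks. These figures assume a beta-binomial model, four assessments and complete data.

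The weekly columns of Exhibit 5.3.1 are sound. The correction is worth making because it supplies the overall part of a stated endpoint at almost no cost.

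**What to change.** In Exhibits 5.3.1–5.3.3:

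1. Keep the pooled Overall column whole, so that the severity rows still add up to presence. Relabel it as a percentage of participant-weeks and state its denominator.
2. Add a separate row or column: participants with the symptom at one or more assessments from baseline to week 4, with a Wilson 95% interval.
3. Report it under both completeness rules used for constipation: all four assessments answered (as in Exhibit 5.2.2) and at least one answered (as in Exhibit 5.2.3). Both matter because fewer answers mean fewer chances to report: at p = 0.25 and ρ = 0.5, two assessments give 34.4% ever affected, against 43.6% with four.
4. State that this figure serves the overall part of SAP item 7 and any comparison with constipation period prevalence.
5. Put no ordinary Wilson interval on the pooled percentage, because it ignores repeated answers from one person.

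Cost: changed footnotes and added rows in three tables, from data already collected. The tables become slightly longer, and any-occurrence figures may approach the ceiling for very common symptoms.
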